8.3. Statistical Analyses

The statistical analysis plan (SAP) will be developed and finalized before database lock for any of the planned analyses. It will describe the participant populations to be included in the analyses and the procedures for accounting for missing, unused, and spurious data. This section provides a summary of the planned statistical analyses of the primary, secondary, and tertiary/exploratory endpoints.

8.3.1.	Part 1 -	• Open	Label	Lead-in	Phase
--------	----------	--------	-------	---------	-------

Endpoint	Statistical Analysis Methods
Primary	Descriptive statistics (counts and percentages) will be used to present the following:
	• Frequency, duration, and severity of solicited symptoms of reactogenicity (local, systemic) for 1 week following each vaccination
	• Frequency, duration, and severity of unsolicited treatment-emergent adverse events (TEAEs), serious AEs (SAEs), and medically attended AEs (MAAEs). MAAEs include (1) active monitoring for COVID-19 and vaccine-associated enhanced disease (VAED), and (2) monitoring for potential immune-mediated medical

Vaxart, I	nc.
-----------	-----

	1
	conditions including AEs of special interest (AESIs) and new onset of chronic illness (NOCIs)
	Descriptive statistics will be provided for each reactogenicity endpoint for each dose and vaccine group. Local reactions and systemic events from Day 1 through Day 8 after each vaccination will be presented by severity and cumulatively across severity levels. Descriptive summary statistics will include counts and percentages of participants with the indicated endpoint and the associated Clopper-Pearson 95% CIs.
Secondary	Frequency, duration, and severity of all SAEs, and MAAEs including monitoring for COVID-19, VAED, AESIs and NOCIs through one year post last dose
	Key immunogenicity endpoints:
	 SARS-CoV2-specific Immunoglobulin G (IgG) and Immunoglobulin A (IgA) antibody levels by Mesoscale Discovery (MSD) assay
	• Neutralizing serum antibody titers to SARS-CoV-2
	Additional immunogenicity endpoints:
	• T cell responses by intracellular cytokine cytometry (ICC)
	Antigen S-specific IgA in nasal swabs
	Antigen S-specific IgA in saliva
	• Anti-Ad5 serum antibodies (optional)
	Geometric mean titers/concentrations (GMTs/GMCs) of SARS-CoV-2 neutralizing titers, S-binding IgG level, , and S-binding IgA levels serum, nasal and saliva), GMTs/GMCs and 2-sided 95% CIs and other reported antigens will be provided for by treatment group at the following time points:
	• Day 1, Week 4, Week 8, Optional (Month 7, and Month 13)
	• Geometric means will be calculated as the mean of the assay results after making the logarithm transformation and then exponentiating the mean to express results on the original scale. Two-sided 95% CIs will be obtained by taking natural log transforms of concentrations/titers, calculating the 95% CI with reference to the t-distribution, and then exponentiating the confidence limits.
	The geometric mean fold rise (GMFR) of SARS-CoV-2 neutralizing titers, S-binding IgG level, and S-binding IgA level. For SARS-CoV-2 neutralizing titers, S-binding IgG levels, and S-binding IgA levels, the GMFRs and 2-sided 95% CIs will be provided by treatment group at the following time points:
	• Week 4, Week 8, Optional (Month 7, and Month 13)
	GMFRs will be limited to participants with non-missing values prior to the first dose and at the postvaccination time point. The GMFR will be calculated as the mean of the difference of logarithmically transformed assay results (later time point – earlier time point) and exponentiating the mean. The associated 2-sided CIs will be obtained by calculating CIs using Student's t-distribution for the mean difference of the logarithmically transformed assay results and exponentiating the confidence limits.

Vaxart, l	Inc.
-----------	------

	Percentage of participants with ≥4-fold rise (or other assessments as per the SAP) in SARS-CoV-2 neutralizing titers, S1-binding IgG level, and RBD-binding IgG level will be summarized by treatment group at the following timepoints.
	• Week 4, Week 8, Optional (Month 7, and Month 13)
	For all the immunogenicity endpoints, the analysis will be based on the Dose 1 and Dose 2 evaluable immunogenicity populations. An additional analysis will be performed based on the all-available immunogenicity populations if there is a large enough difference in sample size between the all-available immunogenicity populations and the evaluable immunogenicity populations. Participants will be summarized according to the vaccine group to which they were randomized.
	Additional immunogenicity data will be assessed as per the SAP. Missing serology data will not be imputed.
Exploratory	Descriptive statistics (counts and percentages) will be used to present the following:
	• Frequency, duration and severity of virologically confirmed COVID-19 illness and serologically confirmed SARS-CoV-2 infection occurring from 7 days following second study drug dose administration

8.3.2. Part 2- Double Blind, Placebo Controlled

Endpoint	Statistical Analysis Methods
Primary: 1. Primary Efficacy	All analyses will be performed at 6 months post last vaccination. The database will be locked and unblinded at this time the efficacy and safety analysis will be conducted.
2. Secondary Efficacy	The evaluable efficacy population will be the primary analysis population for all efficacy analyses. Additional analyses based on the all-available efficacy population will be performed.
3. Safety	1. Primary Efficacy
	Frequency of virologically confirmed COVID-19 illness and serologically confirmed SARS-CoV-2 infection occurring from 7 days following second study drug dose administration.
	Ratio of confirmed COVID-19 illness from 1 week after the Dose 2 per 1000 person-years of follow-up in participants without evidence of infection for the active vaccine group to the placebo group VE will be estimated by $100 \times (1 - IRR)$, where IRR is the calculated ratio of confirmed COVID-19 illness per 1000 person-years follow-up in the active vaccine group to the corresponding illness rate in the placebo group from 1 week after the Dose 2.
	VE will be analyzed using a beta-binomial model. After the above objective is met, the second primary endpoint will be evaluated as below. Ratio of confirmed COVID-19 illness from 1 week after the Dose 2 per 1000 person-years of follow-up in participants with and without evidence of infection (prior to 1 week after

Vaxart,	Inc.
---------	------

receipt of Dose 2) for the active vaccine group to the placebo group VE will be estimated by $100 \times (1 - IRR)$, where IRR is the calculated ratio of confirmed COVID-19 illness per 1000 person-years follow-up in the active vaccine group to the corresponding illness rate in the placebo group from 1 week after the second dose. VE will be analyzed using a beta-binomial model.
The efficacy analysis for the first primary objective evaluation will be based on the participants without evidence of infection before vaccination and included in the evaluable efficacy population and in the all-available efficacy population.
The efficacy analysis for the second primary objective evaluation will be based on all participants included in the evaluable efficacy population and in the all- available efficacy population.
For the primary endpoint analysis, missing efficacy data will not be imputed. A sensitivity analysis will be performed by imputing missing values with the assumption of missing at random (MAR). A missing efficacy endpoint may be imputed based on predicted probability using the fully conditional specification method. Other imputation methods without the MAR assumption may be explored. The details will be provided in the SAP.
2. Secondary Efficacy
First: Ratio of confirmed COVID-19 illness from 1 week after the second dose per 1000 person-years of follow-up in participants without evidence of infection for the active vaccine group to the placebo group.
Second: Ratio of confirmed COVID-19 illness from 1 week after the second dose per 1000 person-years of follow-up in participants with and without evidence of infection for the active vaccine group to the placebo group.
These secondary efficacy objectives will be evaluated sequentially in the order specified above after the primary objectives are met.
The analysis will be based on the evaluable efficacy population. The analysis methodology used for the primary efficacy endpoints will be applied for the analysis of the above secondary efficacy endpoints. The following secondary efficacy endpoints will be evaluated descriptively with 95% CIs. Ratios of confirmed COVID-19 illness (according to the CDC-defined symptoms) from 1 week after the second dose per 1000 person-years of follow-up in participants without evidence of infection for the active vaccine group to the placebo group Ratios of confirmed COVID-19 illness (according to the CDC-defined symptoms) from 1 week after the second dose per 1000 person-years of follow-up in participants with and without evidence of infection for the active vaccine group to the placebo group to the placebo group VE = $100 \times (1 - IRR)$ will be estimated with confirmed COVID-19 illness according to the CDC-defined symptoms from 1 week after the second dose. The 2-sided 95% CI for VE will be derived using the Clopper-Pearson method as described by Agresti (Agresti, 2002). Missing efficacy data will not be imputed.
3. Safety and tolerability
The safety population will be used for all safety analyses.

Vaxart,	Inc.
---------	------

	
	Descriptive statistics will be used to present the following, for each treatment group:
	• Frequency, duration, and severity of solicited symptoms of reactogenicity (local, systemic) for 1 week following each vaccination
	• Frequency, duration, and severity of unsolicited TEAEs, SAEs, and MAAEs through the active period (4 weeks post last dose) efficacy period and safety follow-up period. MAAEs include (1) active monitoring for COVID-19 and VAED through the active period (4 weeks post last dose); and (2) monitoring for potential immune-mediated medical conditions including AESIs and NOCIs for one year post last dose.
Secondary: Long-term Safety	Frequency, duration, and severity of all SAEs, and MAAEs including monitoring for COVID-19, AESIs and NOCIs through one year post last dose
	See section $\underline{8.2}$ (Populations for Analyses) for a descriptive of the populations used for these analyses.
Immunogenicity	Key immunogenicity endpoints:
	• SARS-CoV2-specific IgG and IgA antibody levels using MSD assays
	 Neutralizing serum antibody titers to SARS-CoV-2
	Additional immunogenicity endpoints:
	Antigen S-specific IgA in nasal swabs
	Antigen S-specific IgA in saliva
	Geometric mean titers/concentrations (GMTs/GMCs) of SARS-CoV-2 neutralizing titers, S-binding IgG level, and S- binding IgA level for SARS-CoV- 2 neutralizing titers, S-binding IgG levels, and S-binding IgA levels, GMTs/GMCs and 2-sided 95% CIs will be provided for by treatment group at the following time points:
	• Day 1, Week 4, Week 8, Month 7, and Month 13 after Dose 1
	Geometric means will be calculated as the mean of the assay results after making the logarithm transformation and then exponentiating the mean to express results on the original scale. Two-sided 95% CIs will be obtained by taking natural log transforms of concentrations/titers, calculating the 95% CI with reference to the t-distribution, and then exponentiating the confidence limits.
	GMFRs of SARS-CoV-2 neutralizing titers, S1-binding IgG level, and RBD-binding IgG level. For SARS-CoV-2 neutralizing titers, S1-binding IgG levels, and RBD-binding IgG levels, the GMFRs and 2-sided 95% CIs will be provided by treatment group at the following time points:
	• Day 1, Week 4, Week 8, Month 7, and Month 13 after Dose 1
	GMFRs will be limited to participants with non-missing values prior to the first dose and at the postvaccination time point. The GMFR will be calculated as the mean of the difference of logarithmically transformed assay results (later time point – earlier time point) and exponentiating the mean. The associated 2-sided

Vaxart,	Inc.
---------	------

CIs will be obtained by calculating CIs using Student's t-distribution for the mean difference of the logarithmically transformed assay results and exponentiating the confidence limits.
Percentage of participants with ≥4-fold rise in SARS-CoV-2 neutralizing titers, S1-binding IgG level, and RBD-binding IgG level will be summarized by treatment group.
For SARS-CoV-2 neutralizing titers, S1-binding IgG levels, and RBD-binding IgG levels, percentages (and 2-sided 95% CIs) of participants with \geq 4-fold rise will be provided for by treatment group at the following time points:
• Day 1, Week 4, Week 8, Month 7, and Month 13 after Dose 1
The Clopper-Pearson method will be used to calculate the CIs. GMR of SARS-CoV-2 neutralizing titer to S1-binding IgG level and to RBD-binding IgG level.
For SARS-CoV-2 neutralizing titers, S1-binding IgG levels, and RBD-binding IgG levels, the GMRs and 2-sided 95% CIs will be provided by treatment group at the following time points:
• Day 1, Week 4, Week 8, Month 7, and Month 13 after Dose 1
GMRs will be limited to participants with non-missing values for both SARS- CoV-2 neutralizing titers and S1-binding IgG level/RBD binding IgG level at each time point. The GMR will be calculated as the mean of the difference of logarithmically transformed assay results (e.g., SARS-CoV-2 neutralizing titers minus S1-binding IgG level for each participant) and exponentiating the mean. Two-sided CIs will be obtained by calculating CIs using Student's t-distribution for the mean difference of the logarithmically transformed assay results and exponentiating the confidence limits.
For all the immunogenicity endpoints, the analysis will be based on the Dose 1 and Dose 2 evaluable immunogenicity populations. An additional analysis will be performed based on the all-available immunogenicity populations if there is a large enough difference in sample size between the all-available immunogenicity populations and the evaluable immunogenicity populations. Participants will be summarized according to the vaccine group to which they were randomized.
Missing serology data will not be imputed.

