5.9. Intervention after the End of the Study

Following completion of the study Efficacy period in Part 2, the study database will be cleaned and locked and the treatment assignments unblinded. At this time subjects who were randomized to the placebo group under the current protocol will have the opportunity to receive vaccination(s) against COVID-19 via one of the following options:

- Receipt of an approved COVID-19 vaccine (standard-of care) in the region within which they are located (paid for by the Sponsor), or
- Receipt of a Vaxart oral tableted vaccine for the prevention of COVID-19 under an openlabel extension protocol

The specific approach to be utilized will be further defined and added to the protocol based on the availability of approved COVID-19 vaccines closer to the completion of Part 2.

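### Part 2 Month 13 antibody results are summarised as randomised, although placebo participants are offered COVID-19 vaccine at the six-month unblinding and no rule separates their later samples

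*Combined protocol and SAP*

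**What the plan says.** **Month 13 titres.** In Section 8.3.2 the Part 2 immunogenicity row lists GMTs/GMCs, GMFRs and the percentage with at least a four-fold rise at "Day 1, Week 4, Week 8, Month 7, and Month 13 after Dose 1". On grouping it says: "Participants will be summarized according to the vaccine group to which they were randomized".

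**Placebo vaccination.** Sections 4.2.2 and 4.2.4 place the lock after the last randomised participant's Month 7 visit, and unblinding after the primary efficacy analyses. Section 5.9 continues: "At this time subjects who were randomized to the placebo group under the current protocol will have the opportunity to receive vaccination(s) against COVID-19". One option is "Receipt of an approved COVID-19 vaccine (standard-of care) in the region within which they are located", at the sponsor's cost; the other is the sponsor's oral vaccine under an extension protocol. The choice between them is left for a later protocol addition.

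**Timing of analyses.** The Primary row of 8.3.2, which covers efficacy and safety, opens with "All analyses will be performed at 6 months post last vaccination" and adds "The database will be locked and unblinded at this time the efficacy and safety analysis will be conducted". The safety endpoint in that row includes "monitoring for potential immune-mediated medical conditions including AESIs and NOCIs for one year post last dose". The separate long-term safety row covers "MAAEs including monitoring for COVID-19, AESIs and NOCIs through one year post last dose".

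**The concern.** A placebo participant who accepts the vaccine offered under 5.9 and is then bled at Month 13 contributes a vaccinated person's titre to the placebo column. That participant can even be counted as a placebo responder. The Part 2 immunogenicity objective (Section 4.1) is stated relative to placebo, so a reader will set the two columns side by side. At Month 13 the placebo column would no longer show what happens without vaccination, and any persistence advantage of the oral vaccine would look smaller than it is.

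The second, lesser matter is internal wording. The Primary row ties the safety analysis to the six-month lock, although part of the endpoint in that row needs a year of follow-up. Section 7.2 justifies that year by the theoretical autoimmune risk of the dsRNA adjuvant, so the plan should say plainly when those data are analysed.

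**Working it through.** **Does anything in the plan keep these samples apart?**

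- *Populations (8.2).* The evaluable immunogenicity populations drop important protocol deviations. A vaccination that the protocol itself offers is not a deviation, and the medication prohibitions in 5.6.1 apply only in the Active Period. The all-available population has no such filter.
- *Data collection.* Section 5.6 stops recording concomitant medication four weeks after last dosing, and the medication-review row of Table 4 ends at Week 8. Note c of Table 4 limits follow-up collection to SAEs and MAAEs, so an uneventful vaccination leaves no scheduled entry.
- *Section 5.9.* It leaves the vaccine option open and gives no analysis rule.

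**Whose Month 13 visit follows unblinding?** Measure time from the last participant's randomisation. Unblinding falls at month 7 + d, where d is the lag for cleaning, lock and primary analysis. Someone randomised u months earlier reaches Month 13 at 13 − u. The visit follows unblinding when u < 6 − d. With uniform accrual over A months the share is min(1, (6 − d)/A). The plan gives neither A nor d, so both are assumed. Counts use 341, the efficacy sample size per arm in Section 8.1.2. A two-proportion formula (5% v 0.5%, two-sided 0.05, 95% power) reproduces that figure, and it serves here only as a working number of placebo participants remaining.

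| A (months) | share, d = 0 | of 341 | share, d = 2 | of 341 |
|---|---|---|---|---|
| 3 | 100% | 341 | 100% | 341 |
| 6 | 100% | 341 | 67% | 227 |
| 12 | 50% | 170 | 33% | 114 |
| 24 | 25% | 85 | 17% | 57 |

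The d = 0 columns are upper bounds, since 4.2.4 puts the primary analyses before unblinding.

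**How far could the placebo summary move?** Let p be the fraction of placebo Month 13 samples taken after vaccination, and let each be F times what it would otherwise have been. The mean log titre rises by p·log F, so the GMT is multiplied by F^p. The GMFR moves by the same factor, because baseline is unchanged. Take F = 4, the plan's responder threshold, as an illustration only:

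- p = 25%: 4^0.25 = 1.41
- p = 50%: 4^0.50 = 2.00
- p = 75%: 4^0.75 = 2.83

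Here p is the share after unblinding times uptake. At an assumed 50% uptake, A = 12 and d = 0 give p = 0.50 × 0.50 = 0.25, a factor of 1.41. A = 12 and d = 2 give p = 0.333 × 0.50 = 0.167, a factor of 4^0.167 = 1.26.

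**Secondary point.** At the lock the last participant has 6 of the 12 months observed, so 50% is outstanding. For someone randomised u months earlier the outstanding share is max(0, 6 − u)/12. Averaged over uniform accrual of 3, 6, 12 or 24 months it is 37.5%, 25%, 12.5% or 6.25%.

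**The case against.** *The sentence on analysis timing belongs to the Primary row.* Long-term safety and immunogenicity have their own rows and horizons, and Section 5.8 ends the study at the last participant's last visit. A later analysis is implied. This largely stands. A reader might infer that the one-year safety data would go unanalysed; the documents do not support that. What remains is that the Primary row ties a one-year endpoint to a six-month lock and that no later Part 2 lock is named.

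*No between-arm titre comparison is planned.* This stands. A reader might infer that a vaccine-to-placebo GMT ratio or a test is biased, but 8.3.2 has neither. Its GMR is a within-participant ratio of neutralising titre to binding IgG. Results are shown by arm with confidence intervals, and Week 4, Week 8 and Month 7 samples precede the offer. The harm is to a descriptive comparison at one time point.

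*Recipients are traceable.* This stands in part. The sponsor pays for the approved vaccine or supplies its own, so records should exist, and it would be too strong to say recipients cannot be identified. But no trial data field is named for the date, and a summary cannot separate samples on a date that is not in the database.

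*Section 5.9 is a placeholder, and Section 8.3 defers detail to a SAP still to be written.* This is fair: a handling rule or a later lock could appear there. The SAP cannot create the vaccination record, however, so the collection change belongs in the protocol before unblinding.

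*Excluding samples after vaccination is a choice of estimand.* That is true, and it is why the as-randomised summary should be kept alongside.

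**Conclusion.** The main point holds. As written, Month 13 placebo GMTs, GMFRs and responder rates would mix vaccinated and unvaccinated people among those whose Month 13 visit follows unblinding. That is everyone if accrual takes six months or less with immediate unblinding, and can be fewer with longer accrual or a lag. The inflation factors (1.3 to 2.8 in the cases shown) rest wholly on assumed accrual, lag, uptake and fold rise; they show scale and are not forecasts. The effect is confined to the placebo side of a descriptive Month 13 comparison. A reader might extend it to vaccine-arm persistence or to the efficacy result, but the placebo offer does not alter vaccine-arm titres, and alpha, power and the primary efficacy test are untouched. The as-randomised sentence concerns immunogenicity, so the mixing is not claimed for the safety tables.

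The timing point is a wording conflict. The one-year safety data are deferred, not lost. The plan should be changed on both points, at modest priority for the second.

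**What to change.** 1. **Section 5.6 and Table 4:** record the date and type of any COVID-19 vaccine received, through Month 13.
2. **Section 8.3.2, immunogenicity:** exclude placebo antibody results obtained after first receipt of a COVID-19 vaccine from the main by-group summaries, and show the as-randomised summary as supportive.
3. **Section 8.3.2, safety:** present events after unblinding or after COVID-19 vaccination separately from blinded follow-up.
4. **Section 8.3.2, Primary row:** limit the six-month sentence to efficacy and to safety up to the cut-off. Name a final lock after the last Month 13 visit for one-year SAEs, MAAEs, AESIs and NOCIs and for Month 13 immunogenicity.

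The cost is one data field, one more lock and a table run on data already scheduled. The statistical price is fewer Month 13 placebo samples. If every Month 13 visit follows unblinding, uptake of 25%, 50% or 75% leaves about 256, 170 or 85 of 341. At 50% the placebo interval on the log scale widens by 1/√0.5 = 1.41. Those who stay unvaccinated select themselves, so neither summary is sufficient alone, and safety after unblinding is no longer a blinded comparison.

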4. PART 2 – DOUBLE-BLIND PLACEBO-CONTROLLED

4.1. Part 2 Objectives and Endpoints

Objectives	Endpoints		
Primary			
To assess the efficacy of prophylactic VXA-CoV2-1.1-S against confirmed COVID-19 occurring from 7 days after second dose with a repeat-dose vaccination schedule in healthy adults compared to placebo	• Frequency duration and severity of virologically confirmed COVID-19 illness and serologically confirmed SARS-CoV-2 infection occurring from 7 days following second study drug dose administration		
To evaluate the safety and tolerability of VXA-CoV2-1.1-S with a repeat-dose vaccination schedule in healthy adults compared to placebo	 Frequency, duration, and severity of solicited symptoms of reactogenicity (local, systemic) for 1 week following each vaccination Frequency, duration, and severity of unsolicited TEAEs, SAEs, and MAAEs through the active period (4 weeks post last dose), efficacy period and safety follow-up period. MAAEs will be determined by (1) active monitoring for COVID-19 and VAED through the active period (4 weeks post last dose), and (2) monitoring for potential immune-mediated medical conditions including AESIs and NOCIs for one year post last dose. 		
Secondary			
To assess long-term safety of VXA-CoV2-1.1-S	• Frequency, duration, and severity of all SAEs, and MAAEs including monitoring for COVID-19 and potential VAED, AESIs and NOCIs through one year post last dose.		
To assess the immunogenicity of VXA-CoV2-1.1-S with a repeat- dose vaccination schedule in healthy adults compared to placebo	 Key immunogenicity endpoints: SARS-CoV2-specific IgG and IgA antibody levels using MSD assays Neutralizing serum antibody titers to SARS-CoV-2 Additional immunogenicity endpoints: Antigen S-specific IgA in nasal swabs Antigen S-specific IgA in saliva 		

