8. STATISTICAL CONSIDERATIONS

8.1. Sample Size Determination

8.1.1. Part 1

Part 1 is an open-label, lead in, repeat-dose, dose and age escalation design to evaluate the VXA-COV2-1.1-S oral vaccine in two cohorts with repeat dose administration. Cohort 1 will enroll approximately a total of 36 healthy adult participants that are naive (no prior vaccination against SARS-CoV-2 infection and no history of prior COVID-19 or SARS-CoV-2 infection) across 3 groups of 12 subjects each, encompassing 2 age groups and two dose levels. Cohort 2 will enroll approximately a total of 36 healthy adult participants who have received two doses of an EUA or FDA approved mRNA vaccine for the prevention of SARS-CoV-2 infection across 3 groups of 12 subjects each, encompassing 2 age groups and two dose levels.

There are no sample size calculations utilized for Part 1; the cohort size is estimated to provide informative safety and immunogenicity data to allow dose selection for safely proceeding to Part 2.

8.1.2. Part 2

The number of participants to be randomized in Part 2 (VXA-CoV2-1.1-S and placebo) is predicted to yield meaningful immunogenicity and efficacy results to inform how best to proceed into later stage studies. In previous human studies with Ad5 vectored oral tableted vaccines using the same vaccine platform (Ad5 vectored vaccine coding for target virus-specific antigens and a dsDNA adjuvant), the vaccine was well tolerated at total doses up to $2x10^{11}$ IU.

All testing will be performed at alpha = 0.05. All tests will be two-sided. Assuming attack rate in unvaccinated group (ARU) = 5% and vaccine efficacy (VE) = 90%, 341 participants would be required per treatment arm, yielding 95% power.

The total sample size for Part 2 of this study (2 arms) would be 682. To allow for a $\sim 15\%$ dropout rate, 800 participants will be randomized.

2-sided Alpha	0.05	0.05	0.05	0.05	0.05	0.05	0.05	0.05
ARU	5%	5%	5%	5%	5%	5%	5%	5%
VE	90%	90%	90%	90%	95%	95%	95%	95%
Power	80%	85%	90%	95%	80%	85%	90%	95%
SS/Arm	207	236	276	341	177	202	236	292
Sample Size (part 2 of								
study, two arms)	414		472	682	354	404	472	584

Unvaccinated Atta	ck Rate (ARU): 5%
--------------------------	-------------------

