9.3.2. Definition of MAAE

Medically Attended Adverse Events Definition

MAAEs are defined as TEAEs with medically-attended visits including hospital, emergency room, urgent care clinic, or other visits to or from medical personnel for any reason. Routine study visits will not be considered medically-attended visits. New onset of chronic illness/diseases (NOCI) and AEs of Special Interest (AESIs) will be collected as part of the MAAEs. MAAEs are to be reported for all participants from the moment of vaccination until 12 months after the vaccination. Refer to Appendix 5 (Section 9.5) for list of AESIs that should be monitored in this study.

Events Meeting the TEAE Definition

- Any abnormal laboratory test results (hematology, clinical chemistry, or urinalysis) or other safety assessments (e.g., vital signs measurements), including those that worsen from baseline, considered clinically significant in the medical and scientific judgment of the investigator.
- Exacerbation of a chronic or intermittent pre-existing condition including either an increase in frequency and/or intensity of the condition.
- New conditions detected or diagnosed after study drug administration even though it may have been present before the start of the study.
- Signs, symptoms, or the clinical sequelae of a suspected intervention- intervention interaction.
- Signs, symptoms, or the clinical sequelae of a suspected overdose of either study intervention or a concomitant medication. Overdose per se will not be reported as an AE/SAE unless it is an intentional overdose taken with possible suicidal/self-harming intent. Such overdoses should be reported regardless of sequelae.
- The signs, symptoms, and/or clinical sequelae resulting from lack of efficacy will be reported as TEAE or SAE if they fulfill the definition of TEAE or SAE. "Lack of efficacy" or "failure of expected pharmacological action" also constitutes an TEAE or SAE.

Events NOT Meeting the TEAE Definition

- Events that occurred from consent to pretreatment
- Medical or surgical procedure (e.g., endoscopy, appendectomy): the condition that leads to the procedure is the AE.
- Situations in which an untoward medical occurrence did not occur (social and/or convenience admission to a hospital).
- Anticipated day-to-day fluctuations of pre-existing disease(s) or condition(s) present or detected at the start of the study that do not worsen.

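### Part 2 all-cause safety totals by arm, chiefly MAAEs, include confirmed COVID-19 with no summary that leaves it out, so prevented disease partly offsets vaccine-caused events

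*Combined protocol and SAP*

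**What the plan says.** Section 4.1 makes safety and tolerability compared with placebo a primary objective of Part 2. Section 8.3.2 presents the frequency, duration and severity of unsolicited TEAEs, SAEs and MAAEs descriptively by treatment group, in all randomised participants who received at least one dose.

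COVID-19 enters these classes by two routes.

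- **Through the MAAE definition.** The primary safety text of 8.3.2 reads "MAAEs include (1) active monitoring for COVID-19 and VAED through the active period (4 weeks post last dose". The long-term endpoint in 4.1 covers "MAAEs including monitoring for COVID-19 and potential VAED, AESIs and NOCIs through one year post last dose". The matching row in 8.3.2 also runs to one year but omits VAED. COVID-19 within MAAEs therefore has two end dates.
- **Through the TEAE definition.** Section 9.3.2 says that lack of efficacy "also constitutes an TEAE or SAE".

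Table 7 in section 7.3.1 collects MAAEs and SAEs from first dose to end of study, which spans the whole efficacy window. It stops collecting unsolicited TEAEs 4 weeks after the last dose, although 8.3.2 lists TEAEs through the efficacy and follow-up periods.

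On which visits count, section 9.3.2 says "Routine study visits will not be considered medically-attended visits". Appendix 5 (9.5) repeats the MAAE definition without that exemption. Table 4 requires an unscheduled visit for COVID-19 symptoms or exposure, and neither definition mentions that visit.

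Nowhere is confirmed COVID-19 excluded from a safety count, and no table without it is planned. Section 8.3 leaves detail to a SAP to be finalised before database lock.

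**The concern.** The disease that the vaccine is meant to prevent is also a component of the safety endpoint. If the vaccine works, the placebo arm accumulates more COVID-19, and its all-cause MAAE total rises for a reason unrelated to tolerability. A real excess of other events in the vaccine arm can then look smaller than it is, or vanish, in the total by arm. The totals mix benefit with harm, while the stated objective is tolerability against placebo.

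The visit wording adds uncertainty about what is counted. If a mandatory testing visit makes an illness medically attended, nearly every COVID-19 case becomes an MAAE. If it does not, only cases in which the participant sought care do.

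**Working it through.** **Inputs**

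- Section 8.1.2: two-sided tests at the 0.05 level; a design attack rate of 5% without vaccine and a VE of 90%; the resulting size, "341 participants would be required per treatment arm, yielding 95% power"; and 800 randomised in total, which is 400 per arm at 1:1.
- Section 8.4: alternative VE 80%, attack rate 5%, and a planned split of about 5 vaccine and 26 placebo cases.
- Sections 4.2.2 and 8.3.2: efficacy cases count from 7 days after dose 2 (Day 36) to Month 7, 6 months after the last dose.
- Assumptions: Month 7 falls at about Day 211, so the window is 211 − 36 = 175 days; the 5% attack rate, for which the plan gives no time base, applies to that window; the hazard is constant; there is no protection before Day 36; each participant has one event.

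**1. The plan's own figure.** With p1 = 0.05, p2 = 0.05 × (1 − 0.90) = 0.005 and mean 0.0275, a two-sided pooled-variance test without continuity correction needs

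n = [1.960 × √(2 × 0.0275 × 0.9725) + 1.645 × √(0.05 × 0.95 + 0.005 × 0.995)]² / 0.045² = 341 per arm.

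This matches the plan, and the other per-arm entries in its table also reproduce. The design rates can be used as stated.

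**2. Prevented cases in the efficacy window.** Prevented = N × attack rate × VE.

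| Scenario | Placebo | Vaccine | Prevented |
|---|---|---|---|
| 400 per arm, VE 90% | 20 | 2 | 18 |
| 400 per arm, VE 80% | 20 | 4 | 16 |
| 400 per arm, VE 50% (illustration) | 20 | 10 | 10 |
| 341 per arm, VE 90% | 17.1 | 1.7 | 15.3 |
| Split in section 8.4 | 26 | 5 | 21 |

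**3. Counting from first dose, as the safety tables do.**

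- Day 1 to Month 7: placebo 400 × 0.05 × 211/175 = 24.1; vaccine 400 × 0.05 × (36 + 0.1 × 175)/175 = 6.1. Difference 18.0, or 4.5% of 400. The period before Day 36 adds 20 × 36/175 = 4.1 cases to each arm and cancels.
- Day 1 to Week 8 (Day 57): placebo 20 × 57/175 = 6.5; vaccine 20 × (36 + 0.1 × 21)/175 = 4.4. Difference about 2. This is the window for unsolicited TEAEs in Table 7 and for COVID-19 within MAAEs in the primary safety text.

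**4. Share of cases recorded as MAAEs.** The documents give no share. At assumed shares of 10%, 25%, 50% and 100%, the Month 7 offset is 18 × share = 1.8, 4.5, 9 and 18.

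**5. What the totals would show.** Take 18 vaccine-caused MAAEs, all COVID-19 cases counted (20 placebo, 2 vaccine), and an assumed background rate equal in both arms. Fisher p-values serve only as a yardstick; the plan tests nothing here.

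| Background | COVID-19 included (vaccine v placebo) | COVID-19 excluded | p, excluded |
|---|---|---|---|
| 0% | 20 v 20 | 18 v 0 | 0.000006 |
| 5% | 40 v 40 | 38 v 20 | 0.020 |
| 10% | 60 v 60 | 58 v 40 | 0.066 |
| 20% | 100 v 100 | 98 v 80 | 0.15 |

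With COVID-19 included, the risk ratio is 1.00 in every row.

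**6. SAEs.** Only serious COVID-19 cases offset SAEs. The documents give no rate, so no figure can be derived.

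**The case against.** Several points on the other side stand.

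- **Size.** The figure of 18 does not belong to the primary safety text, which stops COVID-19 within MAAEs at 4 weeks after the last dose; there the gap is about 2. It needs the one-year reading and every case counted. Section 9.3.2 asks for a medically attended visit, and section 4.2.2 only counsels infected participants to notify their physician and to seek care if symptomatic.
- **Reach.** A reader might infer that TEAE, MAAE and SAE comparisons are all distorted by 18, or that immune-mediated harm would be hidden. The documents do not support either. TEAE collection ends at Week 8, and SAEs are limited to serious cases. AESIs are listed by diagnosis and reported in an expedited way, causality is judged for every event, and the Part 2 halting rules for SAEs and unsolicited Grade 3 or higher events rest on related events. The IDMC also sees unblinded data. COVID-19 cannot cancel an imbalance in a named diagnosis.
- **Testing visits.** It is tempting to say that every test-negative cold becomes an MAAE because only routine visits are exempt. That is one reading of an ambiguous definition; nothing states that a mandatory testing visit is medically attended.
- **VAED.** COVID-19 is kept within safety partly to detect enhanced disease. Removing it from the only SAE table could hide that signal. This is right, and it argues for showing both versions.

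Two points carry less weight. The comparison is indeed descriptive, so no formal test is biased, but a total by arm is still read as a comparison. COVID-19 is also reported by arm as an efficacy endpoint, but from 7 days after dose 2 and primarily in the evaluable efficacy population. A reader therefore could not accurately subtract it from MAAE totals counted from first dose in the safety population.

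**Conclusion.** The concern holds for all-cause totals by arm, chiefly MAAEs. Confirmed COVID-19 counts toward them, and no planned summary removes it, so prevented cases partly offset vaccine-caused events. Under the design rates and the assumptions listed above, the offset is:

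- up to about 18 MAAEs to Month 7 if every case is counted, and about 2 to 9 if 10% to 50% are;
- about 2 cases for TEAEs, or for MAAEs limited to Week 8;
- serious cases only for SAEs, with no rate given.

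Lower efficacy or fewer participants followed reduces the offset; the case split in section 8.4 would raise the upper figure to 21. The documents do not support reading this as a bias in a formal test or as a failure of AESI surveillance. It is a cheap improvement to the presentation, together with two passages that need reconciling or clarifying.

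**What to change.** 1. In section 8.3.2 and the SAP, specify the TEAE, MAAE and SAE summaries by arm in two versions side by side, with and without virologically confirmed COVID-19.
2. Tabulate COVID-19, severe COVID-19 and VAED separately by arm, so that enhanced disease stays visible.
3. Reconcile the two end dates for COVID-19 within MAAEs in 8.3.2 (4 weeks after the last dose in the primary text, one year in the long-term row).
4. State in sections 9.3.2 and 9.5 that a protocol-required COVID-19 testing visit does not by itself make an event medically attended.

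The cost is one extra table set and one phrase in the MAAE definition, with no new data, visits or participants. Settling this before unblinding avoids a later choice about which total to feature.
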